8.3 Usage of Concurrent/Concomitant Medications

Supportive medications in accordance with standard practice (such as for emesis, diarrhea, etc.) are permitted. Use of neutrophil growth factors (filgrastim and pegfilgrastim) or red blood cell growth factors (erythropoietin) is permitted per institutional policy and in accordance with the ASCO guidelines ([Smith 2006](#)). Transfusions may be given in accordance with institutional policy.

Short courses (≤ 14 days) of steroid treatment for non-cancer related medical reasons (e.g., joint inflammation, asthma exacerbation, rash, antiemetic use and infusion reactions) at doses that do not exceed 100 mg per day of prednisone or equivalent are permitted.

Treatment for autoimmune cytopenias are permitted for <14 days at doses that do not exceed 100 mg per day of prednisone or equivalent.

Concomitant use of ibrutinib and drugs that inhibit or induce CYP3A should be recorded on the CRF. Use of medications that inhibit platelet function and may increase the risk of bleeding (e.g. Aspirin) should be recorded on the CRF. Use of any medications that may have immunosuppressive effects should be recorded on the CFR.

All AEs and serious AEs (SAEs) that occur on study drug or within 30 days after the last dose of study drug, will be recorded on case report forms (CRFs) from enrollment through 4 weeks post-surgery.

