Grade 2 (increase of 4-6 stools per day over baseline)	Patient should be evaluated by the treating clinician or other physicians including history and physical exam. Infectious work-up include Clostridium difficile and other suspected organisms should be obtained. The patient should be monitored carefully to ensure maintenance of fluid intake to avoid dehydration. If infectious work-up is negative, patient should be managed with supportive therapy including antidiarrheals. If symptoms are prolonged (e.g., >2 weeks) and do not improve with supportive management, reduce the starting dose of ibrutinib by 140mg.
Grade 3 (increase of \geq 7 stools per day over baseline; incontinence; hospitalization indicated)	Hospitalization with management per standard institutional practices. Rule out Clostridium difficile . Hold ibrutinib until diarrhea \leq grade 1, then resume ibrutinib at 50% of the starting dose.
Grade 4 (Life-threatening consequences; urgent intervention indicated)	Urgent hospitalization and medical management per standard institutional practices. Discontinue ibrutinib therapy.
Nausea/Vomiting (very common)	
Grade 1 (loss of appetite without alteration in eating habits; 1-2 episodes of vomiting in 24 hours)	5-HT3 antagonists (e.g., Ondansetron), D2 antagonists (e.g., Prochlorperazine), or other antiemetic, alone or in combination can prevent nausea in the majority of patients. Avoid prescription of steroids (e.g., Prednisone or Dexamethasone) which has

Toxicity and Intensity	Dose Modification and Suggestions for Management
	immunomodulatory effects and may affect study endpoints.
Grade 2 (oral intake decreased without significant weight loss, dehydration or malnutrition; 3-5 episodes of vomiting in 24 hours)	Implement one or more combinations of antiemetics. Avoid prescription of steroids (e.g., Prednisone or Dexamethasone) which has immunomodulatory effects and may affect study endpoints.
Grade 3 (inadequate oral caloric or fluid intake; tube feeding, TPN or hospitalization indicated; ≥ 6 episodes of vomiting in 24 hours)	Hospitalization and supportive management including hydration and caloric intake per standard institutional practices. Hold ibrutinib until nausea \leq grade 1, then resume ibrutinib at 50% of the starting dose after adequate fluid and caloric intake are achieved. Avoid steroids (e.g., Prednisone or Dexamethasone) which has immunomodulatory effects and may affect study endpoints.
Cough (very common)	

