Grade 1 (mild symptoms, nonprescription intervention indicated)	Symptomatic management with OTC cough suppressants (e.g., Robitussin).
Grade 2 (moderate symptoms, medical intervention indicated; limiting instrumental ADL)	Chest imaging as clinically indicated to rule out pneumonia. Trial of prescription cough suppressants (e.g., Benzonatate). If symptoms are prolonged (e.g., >2 weeks) and do not improve, reduce the starting dose of ibrutinib by 140mg.
Grade 3 (severe symptoms; limiting self care ADL)	Chest imaging as clinically indicated to rule out pneumonia. Hospitalization if clinically indicated. Hold ibrutinib until cough \leq grade 1, and any reversible causes (e.g., pneumonia) are fully treated. Then resume ibrutinib at 50% of the starting dose.
Pneumonia (very common)	
Grade 2 (moderate symptoms; oral intervention indicated)	Oral antibiotic, antifungal or antiviral as clinically indicated. Chest imaging if clinically indicated. If symptoms are prolonged (e.g., >2 weeks) and do not improve, reduce ibrutinib starting dose by 140mg.
Grade 3 (IV intervention indicated; radiologic, endoscopic or operative intervention indicated)	Hospitalization for infectious work-up and management including imaging and endoscopic or operative intervention per standard institutional practices. IV antibiotic, antifungal and/or antiviral per standard institutional practices. Hold ibrutinib until pneumonia is fully treated, then resume at 50% of the starting dose.
Grade 4 (life-threatening consequences; urgent intervention indicated)	Hospitalization and management including IV antibiotics, antifungal and/or antiviral per standard institutional practices. Discontinue ibrutinib.
Maculopapular rash (very common)	
Grade 1 (<10% BSA covered with or without symptoms)	Continue dose level of ibrutinib. Review medications for other potential drug etiologies and discontinue agent(s) as appropriate. Use topical or oral antihistamines for symptomatic relief. Topical corticosteroids may be used if clinically indicated. Avoid systemic corticosteroids which has systemic immunomodulatory effects and may affect study endpoints.

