Grade 2 (10-30% BSA covered with or without symptoms; limiting instrumental ADL)	Review medications for other potential drug etiologies and discontinue suspected agent(s) as appropriate. Use topical or oral antihistamines for symptomatic relief. Topical corticosteroids may be used if clinically indicated. Avoid systemic corticosteroids which has systemic immunomodulatory effects and may affect study endpoints. If symptoms are prolonged (e.g., >2 weeks) and do not improve, reduce the starting dose of ibrutinib by 140mg.

Toxicity and Intensity	Dose Modification and Suggestions for Management
Grade 3 (>30% BSA covered with or without symptoms; limiting self care ADL)	Review medications for other potential drug etiologies and discontinue suspected agent(s) as appropriate. Use topical or oral antihistamines for symptomatic relief. Topical corticosteroids may be used if clinically indicated. Avoid systemic corticosteroids which has systemic immunomodulatory effects and may affect study endpoints. Hold ibrutinib until rash \leq grade 1, and then resume at 50% of the starting dose.
Anemia (very common)	
Grade 1 (Hb <LLN-10.0 g/dL)	Maintain ibrutinib dose level. Assess for evidence of gastrointestinal bleeding.
Grade 2 (Hb <10.0-8.0 g/dL)	Assess for evidence of gastrointestinal bleeding. Hold ibrutinib until anemia is resolved to \leq grade 1, at which time resume ibrutinib at 140mg lower than the starting dose.
Grade 3 (Hb <8.0 g/dL, transfusion indicated)	Transfuse PRBC per standard institutional practices. Hold ibrutinib until anemia \leq grade 1, and then resume at 50% of the starting dose. Red blood cell growth factors (erythropoietin) are permitted per institutional policy and in accordance with the ASCO guidelines. Short doses of steroids for autoimmune cytopenias are permitted for <14 days at doses that do not exceed 100 mg per day of prednisone or equivalent.
Thrombocytopenia (very common)	
Grade 1 (Plt <LLN- 75,000/mm ³)	Check manual blood smear to rule out pseudothrombocytopenia. Maintain ibrutinib dose level.
Grade 2 (Plt <75,000-50,000/mm ³)	Check manual blood smear to rule out pseudothrombocytopenia. Hold ibrutinib until thrombocytopenia is resolved to \leq grade 1, at which time resume at 140mg lower than the starting dose.

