8.5 Prohibited Medications/Therapies

The following should not be administered at any time during the study.

- Any investigational product other than ibrutinib.
- Systemic corticosteroid with the exception of a short course of steroids for the management of treatment related autoimmune cytopenias). Topical and inhaled steroids are allowed.
- Anticoagulant including warfarin or other vitamin K antagonists and lower molecular weight heparin (LMWH) including enoxaparin.
- With the exception of aspirin, anti-platelet agents (e.g., clopidogrel, glycoprotein IIb/IIIa inhibitors) are not allowed.
- Vaccine therapy including influenza vaccination. However, COVID-19 vaccines may be allowed at discretion of investigator.
- Hormone therapy including LHRH agonists, antiandrogens (e.g., bicalutamide, flutamide, nilutamide), and 5-α-reductase inhibitors (e.g., finasteride, dutasteride)
- Radiation therapy may not be initiated until after RP.

Should subjects receive one or more of the above medications or therapies, they will remain on study and will continue to receive safety evaluations. Following RP, subjects may receive hormone therapy or radiation therapy as deemed appropriate by their medical professional.

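### Section 8.3 permits systemic steroid courses for five non-cancer reasons that Section 8.5 prohibits, and nothing says which rule prevails

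*Combined protocol and SAP*

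**What the plan says.** Section 8.3 (concomitant medications) permits short courses, at most 14 days and at most 100 mg/day of prednisone or equivalent, of "steroid treatment for non-cancer related medical reasons (e.g., joint inflammation, asthma exacerbation, rash, antiemetic use and infusion reactions"). A separate sentence there allows treatment of autoimmune cytopenias for under 14 days at the same dose cap. Section 8.3 also requires drugs with possible immunosuppressive effects to be recorded.

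Section 8.5 (prohibited therapies) opens its list with "The following should not be administered at any time during the study". The steroid item reads "Systemic corticosteroid with the exception of a short course of steroids for the management of treatment related autoimmune cytopenias", followed by "Topical and inhaled steroids are allowed". Of subjects who receive a listed therapy anyway, it says "they will remain on study and will continue to receive safety evaluations".

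Section 6.3 (toxicity table) says, for grade 3 nausea and vomiting, "Avoid steroids (e.g., Prednisone or Dexamethasone) which has immunomodulatory effects and may affect study endpoints"; the grade 1 and 2 rows and the fatigue rows carry much the same advice. For maculopapular rash it says "Avoid systemic corticosteroids which has systemic immunomodulatory effects and may affect study endpoints", while allowing topical corticosteroids where clinically indicated. Its only systemic allowance is for autoimmune cytopenias; the grade 3 anemia row says "Short doses of steroids for autoimmune cytopenias are permitted for <14 days", and the grade 4 thrombocytopenia row is similar.

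Appendix 2 lists prednisone and dexamethasone under one combined title for prohibited and restricted drugs, without saying which category each belongs to.

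**The concern.** The same prednisone course for, say, an asthma exacerbation is permitted under 8.3 and prohibited under 8.5. Staff cannot tell whether to give it as allowed care or record it as a departure.

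This matters because of what the trial measures. Under 2.2.1, 9.1.2 and 12.3, the phase 2 primary endpoint rests on immune-cell density, B cells above all, in the RP specimen relative to the pre-treatment biopsy. Section 6.3 names steroids as immunomodulatory drugs that may affect the endpoints. Under 12.4 and 12.6.1 every man who receives a dose is analysed for efficacy, and no rule covers men who received steroid. Following 8.3 could therefore place steroid exposure between the two tissue samples being compared.

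**Working it through.** No arithmetic applies. The conflict is between two text rules and depends on no sample size, error rate or response rate. The check sets the sections side by side for systemic steroid.

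| Reason for systemic steroid | 8.3 | 8.5 | 6.3 |
|---|---|---|---|
| Joint inflammation | permitted | prohibited | silent |
| Asthma exacerbation | permitted | prohibited | silent |
| Rash | permitted | prohibited | avoid |
| Antiemetic use | permitted | prohibited | avoid |
| Infusion reaction | permitted | prohibited | silent |
| Autoimmune cytopenia | permitted, under 14 days, up to 100 mg/day | permitted as a short course if treatment-related | permitted, under 14 days, up to 100 mg/day |

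Three ways of reconciling the sections were tried.

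1. *By route.* Inhaled steroid for asthma and topical steroid for rash are allowed by 8.5, and topical steroid for rash by 6.3, so there is no dispute there. But 8.3 caps its courses in mg/day of prednisone equivalent, which is a systemic dose. Route does not remove the conflict.
2. *By scope.* The disputed sentence in 8.3 could be a loose restatement of the cytopenia exception. It is not: 8.3 gives the cytopenia allowance in its own sentence, so the other is an additional permission. The five reasons are also only examples of a wider class of non-cancer reasons.
3. *By precedence.* No section ranks 8.3 against 8.5. The 8.5 sentence about staying on study says what happens to the man, not whether the drug was allowed. Appendix 2 does not separate prohibited from restricted drugs.

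The two sections agree only on autoimmune cytopenias and on topical or inhaled use. Wherever 6.3 addresses one of the five reasons, it agrees with 8.5. It also advises against steroids for fatigue, which 8.3 does not name. Section 8.3 is the outlier.

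The period that matters for the primary endpoint runs from Day 1 to RP, planned for Days 36 to 41 (6.1.3 and 8.2).

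**The case against.** The strongest reply is that the conflict will seldom matter. For rash and nausea, 6.3 already steers staff away from systemic steroid. Ibrutinib is oral, so an infusion reaction has no study-drug trigger. That leaves mainly joint inflammation and asthma, at one center, over about six weeks before RP, with immunosuppressive drugs recorded. All of this stands and limits the reach. It does not settle the rule: the 6.3 column offers suggestions for management, it is silent on three of the five reasons, and recording a course does not decide whether it was allowed.

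Two further objections bear on the repair.

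- Section 6.1.3 says that standard institutional surgical care applies before, during and after RP. The documents do not say whether that care includes steroid. If it does, editing 8.3 alone would leave 8.5 at odds with 6.1.3.
- The 8.5 ban runs through the whole study, including the four weeks of follow-up after RP (3.5). By then the specimen has been taken, and only the later blood sample, used for a secondary endpoint (12.6.3.1), could still be affected. The argument from the primary endpoint covers only the period before RP.

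A reader might infer that following 8.3 would bias the primary result or inflate the false-positive rate. The documents do not support this. They give no direction or size for a steroid effect on B cells in prostate tissue, no expected number of exposed men, and no chance that an exposed man would be classed as a responder. Any revised error rate would rest on invented inputs.

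**Conclusion.** The inconsistency is real and can be verified from the text alone: 8.3 permits systemic courses that 8.5 prohibits, and nothing ranks the two. The protocol's own reasoning in 6.3 points to 8.5 as the intended rule, so 8.3 should change.

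The consequence is a possible, unquantified disturbance of the primary endpoint in a probably small number of men. It could go in either direction, and if steroid has no effect on the tissue counts, the result is untouched. Confidence is high on the conflict and does not extend to any effect on the results.

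The conclusion assumes that the prednisone-equivalent cap in 8.3 means systemic dosing, and that the protection of endpoints stated in 6.3 is also the purpose of the ban in 8.5. The second is an inference, since 8.5 gives no reason.

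**What to change.** Edit 8.3 as follows.

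- Delete the permission for steroid courses for non-cancer reasons and refer to 8.5.
- State that systemic steroid is allowed only as a short course for treatment-related autoimmune cytopenias, and that topical and inhaled steroids are allowed. Keep the limits of under 14 days and up to 100 mg/day of prednisone or equivalent. These come from 8.3 and 6.3; 8.5 sets no number.
- State that the restriction protects the period from Day 1 to RP.
- State whether steroid given as standard perioperative care under 6.1.3 is exempt.
- State that any other systemic course is recorded as a protocol departure and that the man stays on study with continued safety evaluations, as 8.5 already provides.

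Sections 8.3 and 8.5 should carry the same period and the same perioperative statement, so that the edit does not create a new mismatch.

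The sample size, primary analysis and data collection do not change. The cost is that courses for the five listed reasons become recorded deviations. Under Appendix 5, a deviation with potential to harm scientific validity is major, and Appendix 6 requires major deviations to be reported to the institutional review office (HRPO) within 10 working days, so some courses could carry that burden.

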8.3.1 Antiplatelet Agents and Anticoagulants

Use ibrutinib with caution in subjects requiring anticoagulants or medications that inhibit platelet function. In an in vitro platelet function study, inhibitory effects of ibrutinib on collagen-induced platelet aggregation were observed. Supplements such as fish oil and vitamin E preparations should be avoided during treatment with ibrutinib. Bleeding events of any grade, including bruising and petechiae, occurred in subjects treated with ibrutinib. Ibrutinib should be held at least 3 to 7 days pre- and post-surgery depending upon the type of surgery and the risk of bleeding (see [Section 7.7](#)). Subjects with congenital bleeding diathesis have not been studied.

Subjects requiring the initiation of therapeutic anticoagulation therapy (e.g., atrial fibrillation), consider the risks and benefits of continuing ibrutinib treatment. If therapeutic anticoagulation is clinically indicated, treatment with ibrutinib should be held and not be restarted until the subject is clinically stable and has no signs of bleeding. Subjects should be observed closely for signs and symptoms of bleeding. No dose reduction is required when study drug is restarted.

8.4 Dietary Restrictions

Ibrutinib can be taken with or without food at approximately the same time each day. Avoid grapefruit and Seville oranges during ibrutinib treatment as these contain moderate inhibitors of CYP3A. Patients should also avoid supplements such as fish oil and vitamin E preparations as they can cause an interaction with ibrutinib.

8.5 Prohibited Medications/Therapies

The following should not be administered at any time during the study.

- Any investigational product other than ibrutinib.
- Systemic corticosteroid with the exception of a short course of steroids for the management of treatment related autoimmune cytopenias). Topical and inhaled steroids are allowed.
- Anticoagulant including warfarin or other vitamin K antagonists and lower molecular weight heparin (LMWH) including enoxaparin.
- With the exception of aspirin, anti-platelet agents (e.g., clopidogrel, glycoprotein IIb/IIIa inhibitors) are not allowed.
- Vaccine therapy including influenza vaccination. However, COVID-19 vaccines may be allowed at discretion of investigator.
- Hormone therapy including LHRH agonists, antiandrogens (e.g., bicalutamide, flutamide, nilutamide), and 5-α-reductase inhibitors (e.g., finasteride, dutasteride)
- Radiation therapy may not be initiated until after RP.

Should subjects receive one or more of the above medications or therapies, they will remain on study and will continue to receive safety evaluations. Following RP, subjects may receive hormone therapy or radiation therapy as deemed appropriate by their medical professional.

8.6 Restricted Medications

Ibrutinib is primarily metabolized by cytochrome P450 enzyme 3A.

Concomitant use of ibrutinib and drugs that strongly or moderately inhibit CYP3A can increase ibrutinib exposure and should be avoided. Strong inhibitors of CYP3A (e.g., ketoconazole, intraconazole, clarithromycin, telithromycin, nefazadone) and moderate inhibitors (e.g., voriconazole, erythromycin, aprepitant, ciprofloxacin, Diltiazem, fluconazole, verapamil) should be avoided. If the benefit outweighs the risk and a strong CYP3A inhibitor must be used, reduce the ibrutinib dose to 140mg or withhold treatment temporarily (for 7 days or less). If a moderate CYP3A inhibitor must be used, reduce ibrutinib treatment to 140mg for the duration of the inhibitor use. No dose adjustment is required in combination with mild inhibitors. Monitor patient closely for toxicity and follow dose modification guidance as needed.

After discontinuation of a CYP3A inhibitor, resume previous dose of ibrutinib.

Administration of ibrutinib with rifampin, a strong CYP3A inducer, decreases ibrutinib plasma concentrations by approximately 90%. Avoid concomitant use of strong CYP3A inducers (e.g., carbamazepine, rifampin, phenytoin, and St. John's wort). Consider alternative agents with less CYP3A induction. For further information, please refer to the current version of the IB and examples of inhibitors, inducers, and substrates can be found at <http://medicine.iupui.edu/clinpharm/ddis/main-table/>. This website is continually revised and should be checked frequently for updates.

Any medications known to cause QT prolongation should be used with caution; periodic ECG and electrolyte monitoring should be considered.

A standard list of prohibited and restricted medications is provided in Appendix 2.

8.7 Guidelines for Ibrutinib Management with Surgeries and Procedures

Ibrutinib may increase risk of bleeding with invasive procedures or surgery. The following guidance should be applied to the use of ibrutinib in the perioperative period for subjects who require surgical intervention or an invasive procedure while receiving ibrutinib.

8.7.1 Minor Surgical Procedures

For minor procedures (such as a central line placement, skin or needle biopsy, lumbar puncture (other than shunt reservoir access), thoracentesis, or paracentesis) ibrutinib should be held for at least 3 days prior to the procedure and should not be restarted for at least 3 days after the procedure. For bone marrow biopsies that are performed while the subject is on ibrutinib, it is not necessary to hold ibrutinib. A minimum of 3 days between prostate biopsy and start of study drug is required for patients who undergo prostate biopsy.

8.7.2 Major Surgical Procedures

For any surgery or invasive procedure requiring sutures or staples for closure, ibrutinib should be held at least 7 days prior to the intervention (except for emergency procedures) and should be held at least 7 days after the procedure and restarted at the discretion of the investigator when the surgical site is reasonably healed without serosanguineous drainage or the need for drainage tubes.

9 REPORTING AND DOCUMENTATION OF RESULTS

9.1 Evaluation of Activity

9.1.1 Characterization of PBMCs using flow cytometry

The number and frequency of immune cell subsets in the peripheral blood, before, during and after ibrutinib therapy will be assessed. Fluorochrome-labeled antihuman antibodies, including antibodies to CD19, CD25, CD27, CD86, CD3, CD8, CD4, CD25, and FOXP3 will be used. Flow cytometry will be performed in either the Immunomonitoring Lab (IML) or [name] Lab in the Center for Human Immunology and Immunotherapy Programs (CHiiPs) at Washington University.

